2.8.6 Safety evaluation after last administration of study treatment

The SAF will be used for analyses in this section.

Safety data collected after last administration of study treatment includes adverse events, vital signs, routine laboratory parameters and ECG. No safety cutoff date will be applied in the analyses defined in this section. Safety data within the safety cutoff date but after last administration of study treatment will also be included. Only subjects who prematurely discontinue the study treatment will be included.

The number and percentage of subjects with at least one TEAEs that started after the date of last administration of study treatment will be reported by SOC, preferred term, and age group. The subset of subjects in the SAF who had data reported after the date of last administration of study treatment will be included in the analysis and the number of subjects in this subset will be the denominator in calculating the percentage.

Summary statistics for vital signs measurements and changes from baseline. These descriptive summaries will be presented by vital sign parameter, treatment group and visit-window.

Summary statistics for each ECG parameter and change from baseline. These descriptive summaries will be presented by vital sign parameter, treatment group and visit-window.

In addition, subjects with notable lab abnormalities or clinically notable vital signs will be listed.

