Initiation of fingolimod treatment results in a transient decrease in heart rate and infrequently induces atrio-ventricular (AV) block. In MS clinical trials, the mean maximal decrease in heart rate after the first dose intake was 12~ 13 bpm and was seen at ~6 hours post-dose. Heart rates below 40 beats per minute were rarely observed in patients on fingolimod 0.5 mg/day. Heart rate progressively returned to baseline within 1 month of dose initiation despite continued dosing. In addition, a mild increase in blood pressure of approximately 2 mmHg diastolic and 3 mmHg systolic on average. This onset after approximately 1 months of treatment initiation persisted with continued treatment but reversed upon cessation of therapy. Hypertension was reported as an adverse event in 6.5% of patients on fingolimod 0.5 mg/day and in 3.3 % of patients on placebo in the 2-years placebo controlled study.

Liver enzyme elevations were seen in clinical trials. Asymptomatic elevations in serum levels of hepatic transaminases ≥ 3 x upper limit of normal (ULN) and ≥ 5 x ULN, were observed in 8.0% and 1.8% of patients treated with fingolimod 0.5 mg/day respectively compared to 1.9% and 0.9% for patients receiving placebo. The majority of elevations occurred within 12 months of therapy and returned to normal, generally within 2 months of discontinuation of therapy.

Macular edema occurred in 0.5% of patients treated with fingolimod 0.5 mg/day. Approximately 75% of cases occurred within the first 3-4 months of therapy. The macular edema generally improved or resolved spontaneously after drug discontinuation. The risk of developing macular edema appears to be increased in MS patients with a history of uveitis. There is limited data on fingolimod in MS patients with diabetes mellitus. In earlier renal

transplant clinical studies where patients with diabetes mellitus were included, therapy with fingolimod 2.5 mg/day and 5 mg/day resulted in a 2-fold increase in the incidence of macular edema. MS patients with diabetes mellitus are therefore expected to be at a higher risk for macular edema.

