2.1.2 Visit windows

2.1.2.1 Visit windows for treatment period

Visit-windows will be used for both efficacy and safety data summaries by visit. Visit windows define a time period “around” the targeted visit date as defined in the evaluation schedule of the clinical study protocol. Visit-windows are non-overlapping and defined without gaps between

consecutive visit windows. The width of visit windows may vary over the course of the study period.

Baseline assessments are defined in [Section 2.1.1](#) and do not require a visit window.

The purpose of visit windows is to analyze data based on the actual study days (rather than "nominal" visits). E.g. if a subject's Month 1 visit is delayed; it is possible that the Month 1 data be re-aligned to visit-window Month 2 and be summarized under Month 2.

- For **efficacy analyses** all nominal visits (i.e. excluding unscheduled visits) will be mapped into one of the defined visit-windows.

-For **safety analyses** all visits (scheduled and unscheduled) will be mapped to visit windows. Safety data from unscheduled visits may be reported separately if applicable.

It is possible that more than one assessment of a subject fall into a particular visit-window. [Section 2.1.2.3](#) deals with the statistical approaches to handle multiple visits in a given visit-window.

Tables displaying summary statistics "by visit" will also use the term *visit-window* as column header; this is to remind the reviewer that multiple assessments of a subject might be summarized. Below tables provide visit-windows definitions for applicable parameters.

Table 2-3 Visit-windows for MRI

Visit-window	Start day	Target Day	End day
Month 12	1	360	540
Month 24	541	720	900

Table 2-4 Visit-windows for routine laboratory values

Visit-window	Start day	Target Day	End day
Month 1	1	30	60
Month 3	61	90	135
Month 6	136	180	225
Month 9	226	270	315
Month 12	316	360	450
Month 18	451	540	630
Month 24	631	720	810

Table 2-5 Visit-windows for vital signs*

Visit-window	Start day	Target Day	End day
Month 1	1	30	60
Month 3	61	90	135
Month 6	136	180	225
Month 9	226	270	315
Month 12	316	360	405
Month 15	406	450	495
Month 18	496	540	585
Month 21	586	630	675
Month 24	676	720	765

*Data collected from Day 1 protocol scheduled visit will not be mapped to the visit windows due to different data collection on those visits.

Table 2-6 Visit-windows for Electrocardiogram (ECG)

Visit-window	Start day	Target Day	End day
Month 1	1	30	60
Month 3	61	90	135

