2.8 Safety analyses

All safety analyses will be conducted using the SAF. The safety cutoff is defined as 45 days (5 times the half-life of fingolimod, 9 days) after the last dose administration of study drug. Unless

explicitly otherwise stated, only data up to and including the safety cut-off will be included in the analysis and data beyond this time point for a given subject will be excluded from the safety analysis.

The assessment of safety will be primarily based on the frequency of adverse events (including death and non-fatal serious adverse events). Additional safety assessments include laboratory tests, vital sign measures, ECG evaluations, ophthalmic and dermatology. Clinically significant findings in these additional safety assessments and other will be reported as adverse events and analyzed as such.

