2.8.4 Other safety data

2.8.4.1 ECG and cardiac imaging data

ECG data will be collected at selected scheduled visits as specified in [\[Protocol Table 8-1\]](#). Clinically significant findings from ECG evaluations will be reported as AEs and included in the analysis of AEs. ECG parameters include mean heart rate, mean PR interval, mean uncorrected QT interval, mean QRS duration, and QT corrected using Fridericia's correction formula (all as collected on the ECG CRF). Descriptive statistics of each ECG parameter will be provided for each baseline and post-baseline visit-window by age group. Similar summaries will also be provided for change from baseline ECG parameters for each post-baseline visit-window. Criteria in corrected QT interval as defined in [Table 2-10](#) will be provided for each criterion by age group (or listing for the Child group if more appropriate).

Table 2-10 Abnormality criteria for corrected QT interval

	Male subjects	Female subjects
1	>450 msec	>470 msec
2	>500 msec	> 520 msec
3	30 - 60 msec increase from Baseline	
4	>60 msec increase from Baseline	

For first dose administration monitoring, ECG parameters and change from pre-dose in ECG parameters by timepoint during 1st and 2nd dose (if necessary) administration will be summarized by age group. The number and percentage of subjects meeting the criteria in corrected QT interval (at any timepoint post-dose during 1st and 2nd dose (if necessary) administration) will be presented by age group (or listing for the Child group if more appropriate).

For non by-visit summaries, visits defined by visit-windows will not be used. All available data from scheduled and unscheduled visits will be considered.

For the patients who missed the visits, but took off-site ECG evaluations due to COVID19 (lockdown, site issue, subject concern or other), the off-site ECG data will be included to analyze. The sensitivity analysis will be conducted to assess ECG data, with the only change to exclude off-site ECG data. For this sensitivity analysis, number and percentage of patients meeting the criteria in corrected QT interval and the corrected QT interval criteria (at any timepoint post-dose during first/second dose administration) by age group will be presented.

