2.8.4.2 Vital signs

Vital sign measurements include sitting systolic and diastolic blood pressures, sitting pulse, body temperature, height and body weight.

Three sitting measurements of blood pressure (SBP and DBP) and pulse will be taken at each vital sign assessment.

For post-baseline assessments, the blood pressure and pulse values will be the average of the non-missing values of the 3 measurements. If more than one blood pressure/pulse assessment (scheduled or unscheduled) exists in a particular visit-window (as defined in [Section 2.1.2.1](#)),

derivation should follow the rules as defined in [Section 2.1.2.3](#). Derivation of baselines for blood pressure and pulse are provided in [Section 2.1.1](#).

Height will be collected at screening visit only and will only be summarized as demographics. Analyses of vital sign measurements (excluding data collected on Day 1 protocol scheduled visit) using descriptive summary statistics (mean, median, standard deviation, min, max) for the change from baseline for each post-baseline visit-window will be performed. These descriptive summaries will be presented by vital sign parameter and age group. Change from baseline will only be summarized for subjects with both baseline and post-baseline values and will be calculated as:

$$\text{change from baseline} = \text{post-baseline value} - \text{baseline value}$$

The number and percentage of subjects with clinically notable vital signs (at any time post-baseline) will be presented by age group. Listings of clinical notable vital signs during treatment period will be presented by age group.

Clinical notable vital signs values are defined in the table below.

Table 2-11 Vital signs clinically notable values

NOTABLE VITAL SIGNS AND BODY WEIGHT		
Vital Sign Variable	Age	Notable Criteria
Heart Rate (bpm)	< 12 years	>130bpm or Increase of ≥ 15 bpm from baseline Or < 70bpm or Decrease of ≥ 15 bpm from baseline
	≥ 12 years	>120bpm or Increase of ≥ 15 bpm from baseline Or < 50bpm or Decrease of ≥ 15 bpm from baseline
Systolic BP (mmHg)	< 12 years	≥ 125 mmHg or Increase of ≥ 20 mmHg from baseline Or ≤ 70 mmHg or Decrease of ≥ 20 mmHg from baseline
	≥ 12 to < 18 years	≥ 160 mmHg or Increase of ≥ 20 mmHg from baseline Or ≤ 90 mmHg or Decrease of ≥ 20 mmHg from baseline
	≥ 18 years	≥ 180 mmHg or Increase of ≥ 20 mmHg from baseline Or ≤ 90 mmHg or Decrease of ≥ 20 mmHg from baseline

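### SAP 2.8.6 limits the post-treatment safety summaries to early stoppers, so completers' 2-month follow-up vital signs and ECG, and their non-serious TEAEs starting more than 45 days after last dose, reach no by-visit or TEAE table

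*SAP*

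**What the plan says.** **The cutoff.** SAP 2.8 sets a safety cutoff of 45 days after last dose (five 9-day half-lives). Unless "explicitly otherwise stated, only data up to and including the safety cut-off will be included in the analysis". SAP 2.1.1 and 2.8.1 exempt serious events and deaths, and 2.8.2 lists every death up to database lock.

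**The post-treatment section.** SAP 2.8.6 applies no cutoff. It plans TEAE counts, and vital-sign and ECG summaries with change from baseline, after last dose. Its population rule is: "Only subjects who prematurely discontinue the study treatment will be included".

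**The completers' visit.** Protocol section 3 and SAP 1.1 bring completers back 2 months after last dose. Protocol Table 8-1 places that visit at Day 775-785, with vital signs, ECG and AE collection.

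**Wording that bears on the counts.** For vital signs, SAP 2.8.4.2 says: "The number and percentage of subjects with clinically notable vital signs (at any time post-baseline) will be presented by age group". It then says: "Listings of clinical notable vital signs during treatment period will be presented by age group". For ECG, SAP 2.8.4.1 says: "For non by-visit summaries, visits defined by visit-windows will not be used. All available data from scheduled and unscheduled visits will be considered". None of these sentences mentions the cutoff.

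**General statements.** SAP 2.1 says that all data, including those beyond 45 days, are considered for safety analyses of the follow-up period. Protocol section 12 says that the analysis takes in the Safety Follow-up epoch.

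**The concern.** The cutoff and the restriction in 2.8.6 work together. The first removes late data from the main tables. The second removes completers from the only visible section that summarises late non-serious events, vital signs and ECG. The group with a scheduled off-drug visit after a full 24 months of treatment then has no summary of that visit.

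The off-drug tables would describe only people who stopped early. They are a selected group, because protocol 9.1.1 gives adverse events and unsatisfactory effect among the reasons for stopping.

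Two protocol statements give the late data some interest. Section 1.1 says that the blood pressure rise on fingolimod "persisted with continued treatment but reversed upon cessation of therapy". Section 8.4.4.4 says that elimination may take up to two months and asks for vigilance for infection over that time. A non-serious infection starting on day 50 after last dose would be tabulated for an early stopper but not for a completer.

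**Working it through.** **Inputs.** Month 24 visit Day 715-725, target 720, and Follow-up visit Day 775-785, target 780 (protocol Table 8-1 and section 8). Half-life 9 days and cutoff 45 days (SAP 2.8). Month 24 analysis windows: vital signs Day 676-765 (SAP Table 2-5), ECG Day 631-810 (Table 2-6). Month 3 after LDD window: days 2-135 after last dose (Table 2-7). Drop-out allowance 20% of about 100 (SAP 3.1). Assumption: a completer's last dose falls at the Month 24 visit.

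1. **The plan's own figure.** 5 × 9 = 45 days, which reproduces.
2. **Follow-up visit, days after last dose.** Shortest 775 − 725 = 50, target 780 − 720 = 60, longest 785 − 715 = 70.
3. **Cutoff in study days.** 715 + 45 = Day 760 to 725 + 45 = Day 770. Every in-window Follow-up visit is later, by 50 − 45 = 5 to 70 − 45 = 25 days.
4. **Vital-sign window.** It ends on Day 765. The visit falls 775 − 765 = 10 to 785 − 765 = 20 days beyond it, so it would fit no treatment-period window even without the cutoff.
5. **ECG window.** Day 775-785 lies inside Day 631-810. Only the cutoff keeps the off-drug ECG from being eligible for Month 24.
6. **Post-treatment window.** Days 50-70 lie inside days 2-135, so the SAP already has a window that would hold the visit.
7. **Drug remaining at a 9-day half-life.** 0.5^(45/9) = 3.1% at day 45 and 0.5^(60/9) = 1.0% at day 60.
8. **Participants affected.** If drop-out approximates early treatment discontinuation, completers number 100 × (1 − 0.20) = 80, with 90 at 10% drop-out and 70 at 30%. These are upper figures, because they assume that every completer attends.

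**Where completers' late data go under the text:**

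| Data | Destination |
|---|---|
| Serious TEAEs, deaths | Reported regardless of cutoff |
| Non-serious TEAEs up to 45 days after last dose | Main TEAE tables |
| Non-serious TEAEs starting later | AE listing only (2.8.1) |
| Follow-up vital signs and ECG: values and change | No by-visit table; general listings (2.1.2.3) |
| Follow-up values in notable and QTc-category counts | Unclear (2.8.4.1, 2.8.4.2) |

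The dedicated listings of notable vital signs do not clearly help. The one in 2.8.4.2 covers the treatment period, and the one in 2.8.6 falls under that section's restriction.

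**The case against.** **The data may already be included.** SAP 2.1 considers all data for follow-up analyses, and the TEAE denominator in 2.8.6 is the safety-set subjects with data after last dose. Both could signal that completers belong. But 2.1 states a principle, and 2.8.6, the only visible section that carries it out, names early stoppers only. The denominator sentence can sit inside that restriction, so the two sentences in 2.8.6 need not contradict each other. A programmer following the explicit restriction would leave completers out.

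**The counts may catch the late values.** This stands in part. If the wording on all available data and any time after baseline waives the cutoff, late values enter the QTc-category and notable-value counts. A reader might infer that completers' follow-up values appear in listings and nowhere else. The documents do not settle that. Even the generous reading gives no values or change from baseline at Follow-up.

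**The restriction may be deliberate.** Table 2-7 runs to Month 27 after last dose, which suits people followed long after stopping, whereas completers have one visit near day 60. That is a coherent choice, but no reason is visible. SAP section 4, where a departure might be declared, is redacted.

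**The protocol promises little.** Protocol section 12 fixes which data are analysed, not a table for each epoch. Section 12.5.1 presents vital signs only by notable ranges. The ECG case is stronger, because 12.5.1 summarises corrected QT by visit.

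**The stakes are modest.** This also stands. Little drug remains by day 60, all AEs are listed, and 45 days already exceeds the 30-day minimum for AE monitoring in protocol 10.1.1.

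**Conclusion.** The point holds as a reporting gap worth closing. Completers' scheduled follow-up vital signs and ECG, and their non-serious TEAEs starting more than 45 days after last dose, enter no by-visit or TEAE summary. This sits poorly with SAP 2.1 and protocol section 12.

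The size is up to about 80 of 100 participants for vital signs and ECG (70 to 90 for drop-out of 30% to 10%). It rests on two assumptions: last dose at the Month 24 visit, and drop-out close to early treatment discontinuation. A Follow-up visit held off schedule within 45 days of last dose would fall within the cutoff. The number of TEAEs affected cannot be estimated from the documents.

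Three stronger readings are not supported:

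- A reader might take the Follow-up visit as the planned measurement of recovery. No section gives it that purpose, and the safety objective concerns treatment for up to 24 months.
- A reader might infer that 2.8.6 alone waives the cutoff. Serious TEAEs and deaths are exempt elsewhere.
- A reader might see a threat to the main results. Efficacy, serious TEAEs, deaths and TEAEs up to the cutoff are untouched.

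The lack of a post-treatment laboratory summary in 2.8.6 applies equally to early stoppers and is a separate matter.

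**What to change.** Replace the population sentence in SAP 2.8.6 with: *All SAF subjects with safety data after last dose will be included, presented separately for subjects who completed treatment and subjects who stopped early.*

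- Use the existing Month 3 after LDD window, with a footnote that completers are seen at about day 60 although the target day is 90.
- Do not pool TEAE percentages across the two groups. Completers have about 60 days of follow-up, and early stoppers may have many months.
- Keep the 45-day cutoff for the main tables.
- State in 2.8.4.1 and 2.8.4.2 whether the cutoff applies to the QTc-category and notable-value counts.
- If the restriction to early stoppers is intended, say so and give the reason.

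**Cost.** SAP wording, a few more tables on data already scheduled, and one footnote. The downside is that some late AEs unrelated to the drug will be counted in the post-treatment table.

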9.1 Discontinuation

9.1.1 Discontinuation from study treatment and from study

Discontinuation of study treatment for a participant occurs when study treatment is permanently stopped for any reason (prior to the planned completion of the study drug administration, if any) and can be initiated by either the participant or the investigator.

The investigator must discontinue study treatment for a given participant if, he/she believes that continuation would negatively impact the participant's well-being.

Discontinuation from study treatment is required under the following circumstances:

- Participant/guardian decision
- Pregnancy

- Use of prohibited treatment as per recommendations in the prohibited treatment section
- Any situation in which continued study participation might result in a safety risk to the participant

Take into consideration the following to establish the list of circumstances under which study treatment must be discontinued:

- Adverse events, abnormal laboratory values or abnormal test result that indicate a safety risk to the participant. Refer to [Section 16.7](#) for Guidance for safety monitoring
- Unsatisfactory therapeutic effect
- Participant's condition no longer requires study treatment

If discontinuation from study treatment occurs, the investigator should make a reasonable effort to understand the primary reason for the participant's discontinuation from study treatment and record this information.

Participants who discontinue from study treatment should be asked to agree to **return for the end of treatment (EOT) and follow up visits indicated** in the Assessment Schedule [Table 8-1](#) (refer to section 8).

If the participant cannot or is unwilling to attend any visit(s), the site staff should maintain regular telephone contact with the participant, or with a person pre-designated by the participant. This telephone contact should preferably be done according to the study visit schedule.

After discontinuation from study treatment, at a minimum, in abbreviated visits, the following data should be collected at clinic visits or via telephone/email contact:

- New / concomitant treatments
- Adverse Events / Serious Adverse Events

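### SAP 2.8.6: an adverse event report alone can place a discontinuer in the denominator of the post-last-dose AE percentage, so the percentage can be inflated

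*SAP*

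**What the plan says.** SAP 2.8.6 sets up a separate look at safety after the drug is stopped.

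- Population: "Only subjects who prematurely discontinue the study treatment will be included".
- Time limit: "No safety cutoff date will be applied in the analyses defined in this section".
- What counts as post-dose safety data: "Safety data collected after last administration of study treatment includes adverse events, vital signs, routine laboratory parameters and ECG".
- Numerator: "The number and percentage of subjects with at least one TEAEs that started after the date of last administration of study treatment", by system organ class, preferred term and age group.
- Denominator: "The subset of subjects in the SAF who had data reported after the date of last administration of study treatment will be included", and "the number of subjects in this subset will be the denominator in calculating the percentage".

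The section does not require a visit, a contact or a minimum length of follow-up for entry to the denominator.

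Protocol 9.1.1 describes how these people are followed. "Participants who discontinue from study treatment should be asked to agree to" come back for the end-of-treatment (EOT) and follow-up visits. Failing that: "If the participant cannot or is unwilling to attend any visit(s), the site staff should maintain regular telephone contact with the participant". The minimum data set for abbreviated visits or telephone/email contact is new or concomitant treatments and AEs/SAEs; vital signs, laboratory tests and ECG are not part of it. Protocol 10.1.3 adds an event-driven route: SAEs are reportable until 30 days after the last study visit, and after that only if the investigator suspects a causal link to treatment.

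**The concern.** Everyone in the numerator is in the denominator by construction, because their AE is itself a post-dose record. A participant without an AE enters only if something else was recorded after the last dose.

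Take two discontinuers, both followed by telephone only. One reports an infection and counts in both numerator and denominator. The other reports nothing, may leave no record of the kind the section lists, and may drop out of the calculation. Likewise, a participant who surfaces only through a late SAE report adds one to both numerator and denominator. Dropping AE-free people lowers the denominator, and adding event-only cases adds equally to both counts. Each can raise the percentage and neither can lower it.

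At stake is the reading of the SAP's dedicated AE table for discontinuers after stopping drug. Protocol 8.4.4.4 says elimination may take up to two months and asks for vigilance for infection over that time, so the table will be read with interest. It will also be small. If the planned 20% drop-out among about 100 participants is taken as a rough guide, it covers about 100 × 0.20 = 20 people. Study drop-out is not the same as treatment discontinuation, so that figure only sets the scale.

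**Working it through.** The plan states no figure for this percentage, so there is none to reproduce. The check asks when the rule biases the result, and by how much under stated assumptions.

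**Inputs (all assumed; the documents give none of them)**
- p: true risk of an AE starting after the last dose, taken to be the same with and without a visit.
- v: share of discontinuers with an AE-independent post-dose record (visit, laboratory, ECG, vital signs).
- r: chance that an AE in someone without such a record is still reported, for example by telephone or as an SAE.
- An AE-free participant without such a record is taken to have no other record that counts.

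**Formula**
- Numerator share: p[v + (1−v)r]
- Denominator share under SAP 2.8.6: v + (1−v)rp
- Reported percentage: p[v + (1−v)r] / [v + (1−v)rp]

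Dividing by p gives [v + (1−v)r] / [v + (1−v)rp]. Since p is at most 1, this ratio is never below 1. It equals 1 when v = 1 or r = 0.

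**Numbers for p = 30%, r = 1**
- v = 0.9: 0.30 / (0.9 + 0.1 × 0.3) = 0.30/0.93 = 32.3%
- v = 0.8: 0.30 / (0.8 + 0.2 × 0.3) = 0.30/0.86 = 34.9%
- v = 0.5: 0.30 / (0.5 + 0.5 × 0.3) = 0.30/0.65 = 46.2%

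**Reported percentage as r runs from 0 to 1**

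| v | p = 10% | p = 30% | p = 50% |
|---|---|---|---|
| 1.0 | 10.0 | 30.0 | 50.0 |
| 0.9 | 10.0–11.0 | 30.0–32.3 | 50.0–52.6 |
| 0.8 | 10.0–12.2 | 30.0–34.9 | 50.0–55.6 |
| 0.5 | 10.0–18.2 | 30.0–46.2 | 50.0–66.7 |

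**In whole people (assumed):** of 20 discontinuers, 16 have a post-dose assessment (4 with an AE) and 4 are reached by telephone only (1 with an AE). SAP rule: (4 + 1)/(16 + 1) = 5/17 = 29.4%. All followed: 5/20 = 25.0%. If all 20 have a post-dose assessment and 5 have an AE, both rules give 5/20 = 25.0%.

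**Why all discontinuers is not the right denominator either:** that percentage is p[v + (1−v)r]. With p = 30% it runs from 24.0% to 30.0% at v = 0.8 and from 15.0% to 30.0% at v = 0.5. It understates the risk whenever some people were not followed.

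**The case against.** The strongest reply is that the planned follow-up may leave little room for the bias. Protocol 9.1.1 asks discontinuers to return for EOT and follow-up visits, and Protocol Table 8-1 schedules vital signs, ECG, hematology and chemistry at the EOT, end-of-study and follow-up visits. SAP 2.5.3 expects discontinuers to stay in the study and follow the assessment schedule. Any such visit after the last dose brings AE-free people into the denominator. The telephone minimum also includes new treatments, and SAP 2.4.2.1 has a class for medications started after discontinuation, so an AE-free telephone contact could leave a record.

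This stands as a limit on the size, and it rules out a stronger reading. A reader might infer that the incidence is inflated. The documents do not support that, because inflation needs discontinuers who lack an AE-independent record and whose AEs are still reported, and their number is not given.

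It does not remove the problem. Attendance is by agreement. An EOT assessment on the day of the last dose is not after it. Section 2.8.6 does not say whether a medication record or an AE-free call counts as reported data; medications are not in its list.

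A second reply is that the main summaries are untouched, and that is right. SAP 2.8 and 2.8.1 already include TEAEs up to 45 days after the last dose and all serious TEAEs and deaths regardless of the cutoff, and all AEs are listed. A reader might also blame the denominator for the table not being comparable with those summaries. That would be wrong: the table covers only premature discontinuers and applies no cutoff, so it would differ under any denominator.

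**Conclusion.** The point holds as a conditional one. As written, entry to the denominator depends partly on the outcome, so the rule can inflate the percentage of discontinuers with a post-dose TEAE and cannot deflate it. AEs that are never reported would lower the percentage, but that is under-ascertainment and does not come from this rule.

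The size cannot be determined from the documents. With an assumed true risk of 30%, the table would show 30–32% if 90% of discontinuers have an AE-independent record, 30–35% at 80% and 30–46% at 50%. The upper ends assume that every AE in a participant without such a record is still reported, so they are ceilings and not expected values. The lower ends, with no inflation, apply if AEs surface only through visits. If every discontinuer has an AE-independent record there is no inflation at all.

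This affects one descriptive safety table in a small group. The primary endpoint, the sample size and the main TEAE tables are not touched. It is worth correcting because the rule is stated, its direction is known and the change is small.

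**What to change.** In SAP 2.8.6:

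1. Define the denominator as premature discontinuers in the safety set with at least one completed visit or documented telephone/email contact after the last dose date, whether or not an AE was reported.
2. Count separately any participant known after the last dose only through an AE or SAE report.
3. State how many discontinuers had no post-dose follow-up.
4. Give post-dose person-time, or an exposure-adjusted rate, beside the percentage, because no time cutoff applies and follow-up will vary in length.

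Do not use an administrative study disposition date to admit participants. Protocol 9.1.3 keeps a participant from being classed as lost to follow-up until due diligence is complete, so that date can fall after the last dose in someone never observed off drug, which would dilute the percentage.

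The cost is a short SAP edit, a little extra programming, and a check that AE-free telephone and email contacts are recorded in the database. The documents do not describe a field for them.
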